#### **6.4.2. Mixed Model for Repeated Measures**

Mixed Model for Repeated Measures analyses will be performed on continuous endpoints to mitigate the impact of missing data. This approach assumes missing observations are missing-at-random (missingness is related to observed data) and borrows information from patients in the same treatment arm taking into account both the missingness of data through the correlation of the repeated measurements.

Essentially MMRM estimates the treatment effects had all patients remained on their initial treatment throughout the study. For this reason, the MMRM implies a different estimand (hypothetical strategy [ICH E9 R1]) than the one used for NRI on categorical outcomes.

All continuous endpoints will utilize MMRM after applying the primary censoring rule. As sensitivity analyses, all secondary continuous endpoints will also utilize MMRM after applying the secondary censoring rule (Table JAIY.6.1).

#### **6.4.3. Modified Last Observation Carried Forward**

For continuous measure, a modified last observation carried forward (mLOCF) imputation technique replaces missing data with the most recent non-missing post-baseline assessment. The specific modification to the LOCF is data after an intercurrent event will not be carried forward thus the mLOCF is applied after the specified censoring rule is implemented. The mLOCF assumes the effect of treatment remain the same after the event that caused missing data as it was just prior to the missing data event. Analyses using mLOCF require a nonmissing baseline and at least 1 postbaseline measure otherwise the data is missing for analyses purposes. Analyses using mLOCF help ensure the number of randomized patients who were assessed post-baseline is maximized and is reasonable for this data as data directly prior to an intercurrent event (such as initiation of rescue therapy or drop out) is likely a non-efficacious response.

All continuous efficacy and health outcomes endpoints will use with mLOCF imputation methodology with an ANCOVA as sensitivity analyses to the MMRM analyses.

#### **6.4.4. Placebo Multiple Imputation**

The Placebo Multiple Imputation (pMI) methodology will be used as a sensitivity analysis for the analysis of the primary efficacy endpoint (IGA 0 or 1 at Week 16) as well as the key secondary endpoints at Week 16. In these sensitivity analyses the primary censoring rule will be applied.

The pMI assumes that the statistical behavior of drug- and placebo- treated patients after the occurrence of intercurrent events will be the same as if patients were treated with placebo. Thus,

in the effectiveness context, pMI assumes no pharmacological benefit of the drug after the occurrence of intercurrent events but is a more conservative approach than mLOCF because it accounts for uncertainty of imputation, and therefore does not underestimate standard errors, and it limits bias. In the efficacy context pMI is a specific form of a missing not at random analysis and expected to yield a conservative estimate of efficacy.

In the pMI analysis, multiple imputations are used to replace missing outcomes for drug- and placebo-treated patients who have an intercurrent event using multiple draws from the posterior predictive distribution estimated from the placebo arm. The binary outcomes will then be derived from the imputed data.

Data are processed sequentially by repeatedly calling SAS® PROC MI to impute missing outcomes at visits  $t=1, \dots, T$ .

1. *Initialization:* Set  $t=0$  (baseline visit)
2. *Iteration:* Set  $t=t+1$ . Create a data set combining records from drug- and placebo-treated patients with columns for covariates  $\mathbf{X}$  and outcomes at visits  $1, \dots, t$  with outcomes for all drug-treated patients set to missing at visit  $t$  and set to observed or imputed values at visits  $1, \dots, t-1$ .
3. *Imputation:* Run Bayesian regression in SAS® PROC MI on this data to impute missing values for visit  $t$  using previous outcomes for visits 1 to  $t-1$  and baseline covariates. Note that only placebo data will be used to estimate the imputation model since no outcome is available for drug-treated patients at visit  $t$ .
4. Replace imputed data for all drug-treated patients at visit  $t$  with their observed values, whenever available up to permanent study drug discontinuation and/or rescue (if censoring on rescue). If  $t < T$  then go to Step 2, otherwise proceed to Step 5.
5. Repeat steps 1-4,  $m$  times with different seed values to create  $m$  imputed complete data sets.

*Analysis:* For continuous endpoints, fit its treatment response model (MMRM) for each completed data set. For the primary and secondary key efficacy endpoints [IGA (0,1), EASI75, EASI90, SCORAD75, and 4-point improvement from baseline in Itch NRS], the binary outcomes will be derived from the imputed data for each patient before fitting the logistic regression model.

The number of imputed data sets will be  $m=100$  and a 6-digit seed value will be pre-specified for each analysis. Within the program, the seed will be used to generate the  $m$  seeds needed for imputation. The initial seed values are given in [Table JAIY.6.2](#).

**Table JAIY.6.2. Seed Values for Multiple Imputation**

Analysis	Seed value
Proportion of patients achieving IGA of 0 or 1 with a $\geq 2$ -point improvement from baseline at Week 16 using the primary censoring rule	123450
Percent change from baseline in EASI score at 16 weeks using the primary censoring rule. EASI75 and EASI90 will leverage imputation from EASI and therefore do not need a new seed number.	123451
Proportion of patients achieving SCORAD75 at 16 week using the primary censoring rule, with data up to rescue	123452
Proportions of patients achieving a 4-point improvement from baseline in Itch NRS at Week 16 using the primary censoring rule	123453
Mean change from baseline in Skin Pain NRS at Week 16 using the primary censoring rule	123454
Mean change from baseline in the score of Item 2 of the ADSS at Week 16 using the primary censoring rule	123455

Abbreviations: ADSS = Atopic Dermatitis Sleep Scale; EASI = Eczema Area and Severity Index score; IGA = Investigator's Global Assessment for AD; NRS = Numeric Rating Scale; SCORAD = SCORing Atopic Dermatitis.

The final inference on treatment difference is conducted from the multiple datasets using Rubin's combining rules, as implemented in SAS® PROC MIANALYZE.

#### **6.4.5. Tipping Point Analyses**

To investigate the missing data mechanism, sensitivity analyses using multiple imputation (MI) under the missing not at random assumption will be provided for the following primary and key secondary objectives as given in [Table JAIY.6.3](#).

All patients in the ITT population will be included. Data after the occurrence of intercurrent events (after application of the primary censoring rule) will be set to missing.

Within each analysis, a most extreme case will be considered, in which all missing data for patients randomized to baricitinib 2 mg or 4 mg will be imputed using the worst possible result and all missing data for patients randomized to placebo will be imputed with the best possible result. Treatment differences will be analyzed using logistic regression or ANCOVA (Section [6.1](#)) as appropriate.

For continuous variables, the following process will be used to determine the tipping point:

1. To handle intermittent missing visit data, a Markov chain Monte Carlo method (SAS® Proc MI with MCMC option) will be used to create a monotone missing pattern.
2. A set of Bayesian regressions (using SAS® Proc MI with MONOTONE option) will be used for the imputation of monotone dropouts. Starting from the first visit with at least 1 missing value, the regression models will be fit sequentially with treatment as a fixed effect and values from the previous visits as covariates.

3. A delta score is added to all imputed scores at the primary time point for patients in the baricitinib treatment groups, thus worsening the imputed value. The delta score is capped for patients based on the range of the outcome measure being analyzed.
4. Treatment differences between baricitinib and placebo are analyzed for each imputed dataset using ANCOVA (Section 6.1). Results across the imputed datasets are aggregated using SAS® Proc MIANALYZE in order to compute a p-value for the treatment comparisons for the given delta value.
5. Steps 3 and 4 are repeated, and the delta value added to the imputed baricitinib scores is gradually increased. The tipping point is identified as the delta value which leads to a loss of statistical significance (aggregated p-value >0.05) when evaluating baricitinib relative to the placebo group.

As a reference, for each delta value used in Steps 3 through 5, a fixed selection of delta values (ranging from slightly negative to slightly positive) will be added to imputed values in the placebo group, and Step 4 will be performed for the combination. This will result in a 2-d table, with the columns representing the delta values added to the imputed placebo responses, and the rows representing the delta values added to the imputed baricitinib responses. Separate 2-d tables will compare each baricitinib dose group to placebo.

A similar process will be used for the categorical variables:

1. Missing responses in the baricitinib groups will be imputed with a range of low response probabilities, including probabilities of 0, 0.1, and 0.2.
2. For missing responses in the placebo group, a range of response probabilities (for example, probability = 0, 0.2 ... 1) will be used to impute the missing values. Multiple imputed datasets will be generated for each response probability.
3. Treatment differences between baricitinib and placebo are analyzed for each imputed dataset using logistic regression (Section 6.1). Results across the imputed datasets are aggregated using SAS® Proc MIANALYZE in order to compute a p-value for the treatment comparisons for the given response probability. If the probability values do not allow for any variation between the multiple imputed datasets (for example, all missing responses in the placebo and baricitinib groups are imputed as responders and nonresponders, respectively), then the p-value from the single imputed dataset will be used.

The tipping point is identified as the response probability value within the placebo group that leads to a loss of statistical significance when evaluating baricitinib relative to placebo.

For tipping point analyses the number of imputed data sets will be  $m=100$  and the seed values to start the pseudorandom number generator of SAS Proc MI (same values for MCMC option and for MONOTONE option) are given in [Table JAIY.6.3](#).

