Treatment comparisons of discrete efficacy variables will be made using a logistic regression analysis with treatment, baseline disease severity, and region in the model. The proportions and 95% confidence interval (CI) will be reported. If a patient needs to use rescue medication, the data after rescue onward will be considered missing and missing data will be imputed using the nonresponder imputation (NRI) method. All patients who discontinue the study or study treatment at any time for any reason will be defined as nonresponders for the NRI analysis for categorical variables after discontinuation onward. Additional analyses will be done using all observed data whether rescue medication was used or not.

Treatment comparisons of continuous efficacy and health outcome variables will be made using mixed-effects model of repeated measures (MMRM) with treatment, region, baseline severity, visit, and treatment-by-visit interaction as fixed categorical effects and baseline score and baseline score-by-visit interaction as fixed continuous effects. An unstructured covariance matrix will be used to model the within-patient variance-covariance errors. Type III sums of squares for the least squares means (LSMs) will be used for the statistical comparison and contrasts will be set up within the model to compare treatment groups at specific time points of interest.

Fisher exact test will be used for all adverse events (AEs), baseline, discontinuation, and other categorical safety data. Continuous vital signs and laboratory values will be analyzed by an analysis of covariance (ANCOVA) with treatment and baseline values in the model.

2. Schedule of Activities

Table JAIY.1. I4V-MC-JAIY Schedule of Activities

	Screening	Double-Blind, Placebo-Controlled							Post-treatment Follow-up
	Period 1	Period 2							Period 3
Visit Number	1	2	3	4	5	6	7	8	801 ^a
Weeks from Randomization		0	1	2	4	8	12	16 or ET	
Days from Randomization		0	7	14	28	56	84	112	
Visit Tolerance Interval (days)	-8 to -35		±2	±2	±2	±4	±4	±4	28 ± 4 after last dose
Procedure									
Inclusion and exclusion review	X	X							
Informed consent	X								
Clinical Assessments									
Demographics	X								
Medical history	X								
Substance Use (alcohol, tobacco use)	X								
Previous and current AD treatments	X								
Weight	X	X			X	X	X	X	X
Height		X							
Vital signs (BP and pulse rate)	X	X	X	X	X	X	X	X	X
Physical examination	X								
Symptom-directed physical examination ^b		X	X	X	X	X	X	X	X

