5.4. Scientific Rationale for Study Design

This study will enroll moderate to severe AD patients with a history of inadequate response to existing topical therapies for whom a systemic treatment such as baricitinib may therefore be appropriate.

Topical corticosteroids are the first-line anti-inflammatory treatment, even for patients treated with systemic treatments. For this reason, this study will assess the efficacy of baricitinib in combination with background mild-to-moderate potency TCS, used as determined appropriate by the investigator.

During the screening period (Period 1), a washout of systemic and topical treatments for AD was incorporated prior to randomization to minimize confounding effects of patients receiving a wide range of different background treatments prior to study entry as well as potential safety issues related to the use of other therapies, including rebound effects after discontinuation of systemic therapies. The double-blind, placebo-controlled treatment period (Period 2) is designed to minimize bias in the evaluation of the efficacy and safety of 2 baricitinib doses, relative to placebo, through 16 weeks of treatment.

In consideration of the disease severity, all patients in Study JAIY are eligible for rescue to higher potency TCS. Investigators are allowed to rescue patients who are experiencing unacceptable or worsening symptoms of AD. Once rescue medication is used, the patient will be determined to be a nonresponder (Section 7.7.4).

Investigator's Global Assessments are commonly used in clinical trials, both for qualifying patients for enrollment and for evaluating treatment efficacy (Langley et al. 2015; Futamura et al. 2016). There is no single "gold standard" disease severity scale for AD; however, IGA scales provide clinically meaningful measures to patients and investigators that are easily described and that correspond to disease severity categories (e.g., moderate to severe). The scale that will be used in this study, the validated Investigator's Global Assessment of Atopic Dermatitis (vIGA-AD, referred to throughout the protocol as IGA), has been developed internally and assesses AD severity using a 5-point scale.

The 16-week efficacy endpoint was chosen because it is likely that a robust clinical effect will be observed with baricitinib within this timeframe based on the Phase 2 study results in AD and from previous studies in another inflammatory skin condition.

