When evaluating continuous measures over time, a restricted maximum likelihood-based mixed-effects model of repeated measures (MMRM) will be used. The model will include treatment, region, baseline severity, visit, and treatment-by-visit interaction as fixed categorical effects and baseline score and baseline score-by-visit interaction as fixed continuous effects. An unstructured (co)variance structure will be used to model the between- and within-patient errors. If this analysis fails to converge, other structures will be tested. The Kenward–Roger method will be used to estimate the degrees of freedom. Type III sums of squares for the least squares means (LSMs) will be used for the statistical comparison; 95% CI will also be reported. Contrasts will be set up within the model to test treatment groups at specific time points of interest. Further details on the use of MMRM will be described in the SAP.

Treatment comparisons of continuous efficacy and health outcome variables may also be made using analysis of covariance (ANCOVA) with region, disease severity, treatment group, and baseline value in the model. Type III tests for LSM will be used for statistical comparison between treatment groups. The LSM difference, standard error, p-value, and 95% CI may also be reported. The method used to handle missing data will be specified in the SAP.

Fisher exact test will be used for the AEs, discontinuation, and other categorical safety data for between-treatment group comparisons. Continuous vital signs, body weight, and other continuous safety variables including laboratory variables will be analyzed by an ANCOVA with treatment and baseline value in the model. Shift tables for categorical safety analyses (e.g., “high” or “low” laboratory results) will also be produced.

Missing data imputation:

1. Nonresponder imputation (NRI): All patients who discontinue the study or the study treatment at any time for any reason will be defined as nonresponders for the NRI analysis for categorical variables such as IGA 0/1 or EASI 50/75/90 after discontinuation and onward. Patients who receive rescue therapy will be analyzed as nonresponders after rescue and onward. An additional analysis will be performed that includes all available data whether rescue medication was given or not.

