## 4. Study Objectives

### 4.1. Primary Objective

The primary objective of this study is to test the hypothesis that baricitinib 4 mg once daily (QD) plus topical corticosteroids (TCS) or baricitinib 2 mg QD plus TCS is superior to placebo plus TCS in the treatment of patients with moderate to severe atopic dermatitis (AD), as assessed by the proportion of patients achieving the validated Investigator's Global Assessment for AD (vIGA-AD, referred to throughout the SAP as IGA) of 0 or 1 with a  $\geq 2$ -point improvement at Week 16.

In particular, the associated estimand for this objective is to measure the effect of therapy with baricitinib as assessed by the proportion of patients with a response of IGA 0 or 1 at Week 16 assuming treatment response disappears after patients are rescued or discontinued from the study or treatment. See Sections 6.4.1 and 6.12.1 on how this estimand handles outcomes after the occurrence of any intercurrent event through nonresponder imputation (NRI).

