### **6.4.1. Nonresponder Imputation**

A nonresponder imputation (NRI) method imputes missing values as non-responses and can be justified based on the composite strategy for handling intercurrent events (ICH E9 R1). This imputation procedure assumes the effects of treatments disappear after the occurrence of an intercurrent event defined by the associated censoring rule.

All categorical endpoints will utilize the NRI method after applying the primary censoring rule to patients who permanently discontinued study drug or were rescued (described in Section 6.4). Additionally, all primary and key secondary categorical endpoints will utilize NRI after applying the secondary censoring rule as sensitivity analyses. For analyses which utilize either of the censoring methods, randomized patients without at least 1 post-baseline observation will be defined as nonresponders for all visits.

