### **6.12.1. Primary Outcome and Methodology**

The validated Investigator's Global Assessment for AD (IGA) uses the clinical characteristics of erythema, papulation/induration, oozing/crusting and lichenification to produce a single-item score ranging from 0 to 4. The primary analysis of the study is to test the null hypotheses that neither baricitinib 4 mg nor baricitinib 2 mg is superior to placebo when evaluating the proportion of patients achieving IGA of 0 or 1 at Week 16 in the ITT population. The analysis assumes that treatment response disappears after patients are rescued or permanently discontinued from treatment. This will serve as the primary estimand. In this estimand, missing data due to the application of the primary censoring rule and the occurrence of other non-censor intercurrent events will be imputed using the NRI method described in Section 6.4.1.

A supplemental estimand is to test the null hypotheses that neither baricitinib 4 mg nor baricitinib 2 mg is superior to placebo when evaluating the proportion of patients achieving IGA of 0 or 1 at Week 16 in the ITT population. This analysis assumes the treatment response disappears after patients permanently discontinued from treatment. In this supplemental estimand, missing data due to the application of the secondary censoring rule and the occurrence of other non-censor intercurrent events will be imputed using the NRI method described in Section 6.4.1.

A logistic regression analysis as described in Section 6.2.3 will be used for the comparisons. The odds ratio, the corresponding 95% CIs and p-value, as well as the treatment differences and the corresponding 95% CIs, will be reported.

Multiplicity controlled analyses will be performed on the primary and key secondary (see Section 4.2.1) objectives to control the overall Type I error rate at a 2-sided alpha level of 0.05. A graphical approach will be used to perform the multiplicity controlled analyses as described in Section 6.6.

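### For the responder endpoints, the tipping-point grid imputes possible response to patients whom the estimand counts as nonresponders, so a tip cannot be attributed to missing data alone

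*SAP*

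**What the plan says.** **The estimand.** SAP 6.12.1, on the primary endpoint: "The analysis assumes that treatment response disappears after patients are rescued or permanently discontinued from treatment". SAP 4.1 words the same idea more widely: "assuming treatment response disappears after patients are rescued or discontinued from the study or treatment". SAP 6.4.1 says that nonresponder imputation (NRI) "can be justified based on the composite strategy for handling intercurrent events". Protocol 5.4: "Once rescue medication is used, the patient will be determined to be a nonresponder". Protocol 10.3.1: "Patients who receive rescue therapy will be analyzed as nonresponders after rescue and onward". The same paragraph of Protocol 10.3.1 also makes a nonresponder of anyone who leaves the study or stops study treatment, whatever the reason.

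**The tipping-point analysis.** SAP 6.4.5 gives its aim as "To investigate the missing data mechanism", under a missing-not-at-random assumption. It then says: "Data after the occurrence of intercurrent events (after application of the primary censoring rule) will be set to missing". The primary censoring rule (SAP 6.4) removes data after rescue and after permanent stopping of study drug. For categorical endpoints, all the resulting gaps are filled at response probabilities of 0, 0.1 and 0.2 on baricitinib and, for example, 0, 0.2, and so on up to 1 on placebo. A most extreme case sets all baricitinib gaps to the worst result and all placebo gaps to the best. Nothing in 6.4.5 holds rescued or discontinued patients at nonresponse. Table JAIY.6.3 lists IGA (0,1), EASI75, EASI90, Itch NRS 4-point improvement and SCORAD75, all under the primary censoring rule.

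**Text that supports the present grid.** The Protocol Synopsis says that for rescued patients "the data after rescue onward will be considered missing" and is then imputed by NRI.

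**The concern.** Under a composite strategy, rescue or stopping study drug is itself the outcome: nonresponse. No value is unknown. The grid nevertheless gives these patients a chance of response and pools them with patients whose Week 16 status really is unknown. Every cell except the one with probability 0 in both arms therefore changes two things at once: how rescue and discontinuation are handled, and what is assumed about absent data.

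No other planned analysis separates the two. Table JAIY.6.1 runs the tipping point only under the primary rule. Placebo multiple imputation (SAP 6.4.4) fills the same pooled set. NRI under the secondary censoring rule restores data after topical rescue, but systemic rescue requires permanent discontinuation of study drug (SAP 6.10), so those patients stay censored, and every absent value stays a nonresponse.

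If the primary result tips, the study report could not say whether the cause was absent Week 16 data or a changed treatment of rescue and discontinuation.

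**Working it through.** **1. The plan's own figure.** SAP 6.1 gives 89% power for a 20-point difference over 10% on placebo, Fisher's exact test, 2-sided alpha 0.025; SAP 5.1 gives 100 per arm. Exact enumeration gives 89.1%, so the planning rates 30/100 versus 10/100 are a sound base for illustration.

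**2. Method.** Log odds ratio with 0.5 added to each cell (Firth's correction in a 2×2 table):

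log OR = ln[(b + 0.5)(100 − p + 0.5) / ((100 − b + 0.5)(p + 0.5))], with variance equal to the sum of the four reciprocals, where b and p are responders on baricitinib and placebo.

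Imputed cells are combined by Rubin's rules with m = 100, enumerating the binomial imputations exactly. The threshold is 0.05 (SAP 6.2). There are no covariates, unlike the planned model with region and baseline IGA. The documents give no rescue, discontinuation or missingness counts, so **all counts below are assumed**.

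**3. Cell with probability 0 in both arms.** b = 30, p = 10: log OR = ln[(30.5 × 90.5)/(70.5 × 10.5)] = 1.316, SE 0.391, p-value 0.0008. This is the primary NRI result.

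**4. Most extreme case** (baricitinib gaps nonresponse, placebo gaps response).
- 7 placebo values: ln[(30.5 × 83.5)/(70.5 × 17.5)] = 0.725, SE 0.341, p-value 0.033.
- 8 placebo values: ln[(30.5 × 82.5)/(70.5 × 18.5)] = 0.657, SE 0.336, p-value 0.051.

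The result tips at 8 imputed placebo responses, whatever made them missing. Fisher's exact test also needs 8. With a smaller observed effect it takes fewer: 5 at 26 versus 10, and 4 at 30 versus 14.

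**5. Present grid, 25 placebo and 10 baricitinib values pooled.** It first exceeds 0.05 at placebo probability 0.4 in all three baricitinib rows: p = 0.140, 0.110, 0.086.

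**6. Same 25, varying only those missing for other reasons.** At baricitinib probability 0, only the placebo count matters.

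| Of the 25 placebo values, missing for other reasons | First tip at placebo probability |
|---|---|
| 5 | never (largest p = 0.013) |
| 10 | 0.8 (p = 0.058) |
| 15 | 0.6 |
| 20 or 25 | 0.4 |

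One printed tip at 0.4 is compatible with every row.

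**7. Smaller counts.** With 20 placebo and 10 baricitinib patients rescued or discontinued and 3 further values missing per arm, the present grid tips at 0.4 (p = 0.11), while the restricted grid never does (largest p = 0.005). With 6 missing per arm, the present grid again tips at 0.4 (p = 0.16) and the restricted maximum is 0.021.

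**8. Which patients are fixed by the estimand?**
- Protocol 10.3.1 and the Synopsis: leaving the study or treatment, for any reason, is nonresponse. SAP 4.1 agrees.
- SAP 6.2.1 treats loss to follow-up as a reason for leaving the study.
- SAP 6.12.1 names rescue and treatment discontinuation only.
- SAP 6.4 lists discontinuation and loss to follow-up as events outside the censoring rules.

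On the Protocol reading, patients lost to follow-up are fixed nonresponders. What remains is patients still in the study, on drug and not rescued, but without a Week 16 value: a missed visit or, for Itch NRS, fewer than 4 diary entries (SAP 6.2.2).

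**The case against.** The strongest reply is that the SAP treats these outcomes as missing data under an assumption. SAP 6.12.1 speaks of data missing through the censoring rule and imputed by NRI; SAP 6.4.1 calls NRI an imputation that assumes the effect is lost; the Synopsis calls post-rescue data missing; and SAP 6.4 counts missed visits among intercurrent events. On that view the grid tests the NRI assumption as a whole. This stands as a defence of keeping the grid. It does not make the grid a test of the missing-data mechanism alone, which is its stated aim, nor does it remove the composite wording in SAP 6.4.1 and Protocol 5.4.

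Second, the set left to vary may be very small. Week 16 is the last treatment visit, and an unscheduled assessment within 4 days can replace a missed one (SAP 6.2.2). On the Protocol reading, the table rows with 10 or more such placebo values look unlikely. This stands, and it limits the benefit.

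Third, SAP 6.7 and 6.10 already report disposition and rescue by arm. They show how many patients were rescued or discontinued, but not, endpoint by endpoint, how many Week 16 values are absent for other reasons, or whether those alone would tip the adjusted model. Protocol 10.3.1 also plans an analysis of all available data regardless of rescue; that varies the handling of rescue, not the absent values.

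A reader might go further and infer that the analysis is invalid, that it could give false reassurance, or that any tip would be produced by rescued patients. The documents support none of these. In the unadjusted table, if the most extreme case stays significant in favour of baricitinib, any restricted grid must too. Without event counts, nobody can say what would drive a tip.

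**Conclusion.** The point holds as a limit on interpretation. SAP 6.4.5 pools outcomes the estimand fixes as nonresponse with outcomes that are unknown, and no planned analysis varies only the latter. A tip is therefore ambiguous; survival is not. The primary test, its alpha and the sample size are untouched.

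The size depends on counts the documents do not give. Under the assumed 25 and 10 pooled values, a tip at 0.4 could mean that absent data could never overturn the result or that they readily could. With equal pools there is no difference. At 30/100 versus 10/100, with baricitinib gaps as nonresponse, fewer than 8 otherwise-missing placebo values cannot tip the result at 0.05. These figures rest on an unadjusted 2×2 analysis.

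It is also tempting to treat loss to follow-up as plainly missing data to be varied. Protocol 10.3.1, the Synopsis and SAP 4.1 do not support that: they make study discontinuation for any reason a nonresponse. Only the narrower wording of SAP 6.12.1 would allow it.

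**What to change.** In SAP 6.4.5, for the responder endpoints:

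1. Add a tipping-point grid that holds as nonresponders all patients with an earlier event the estimand defines as nonresponse: rescue, permanent discontinuation of study drug and, following Protocol 10.3.1, the Synopsis and SAP 4.1, study discontinuation for any reason, including loss to follow-up. Apply the response probabilities only to the remaining Week 16 values (missed visit, or too few diary entries for Itch NRS).
2. Reconcile SAP 6.12.1 (treatment only) and the list of non-censor events in SAP 6.4 with Protocol 10.3.1 and SAP 4.1. If the sponsor keeps the 6.12.1 reading, patients lost to follow-up move into the varied set.
3. Report, per arm and endpoint, how many Week 16 values fall in each set.
4. Keep the present grid as a supplementary stress test, labelled as also varying the handling of rescue and discontinuation. Use the existing 0.05 criterion for both.

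Cost: some SAP wording, one data flag and one more table. If few values are otherwise missing, the added grid will survive almost automatically and tell the reader little beyond the counts. Nothing changes in the primary analysis, sample size or conduct.
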